8.10 Concomitant Therapy and Procedures

The use of concomitant therapies or procedures defined below must be recorded on the patient's CRF. AEs related to administration of these therapies or procedures must also be documented on the appropriate CRF.

8.10.1 Concomitant Therapy

A concomitant therapy is any non-protocol specified drug or substance (including over-the-counter medications, herbal medications and vitamin supplements) administered between signing of informed consent and Week 91 visit.

Allowed Concomitant Therapy

Any medications deemed necessary by the Investigator are allowed except those listed in the disallowed concomitant therapy.

Disallowed Concomitant Therapy

Patients are required to take daily RDA supplemental doses of vitamin A during the treatment and post-treatment evaluation periods. The vitamin A supplements will be provided by the Study Center or designee. A patient may choose to substitute the Study Center provided vitamin A supplement with their own, only after consultation with the Study Medical Monitor. Additional vitamin A supplements (other than those described above) are not allowed at any time during the study unless approved by the Study Medical Monitor (this includes multivitamin supplements that contain vitamin A).

Doxycycline, and tauroursodeoxycholic acid (TUCA) are not allowed unless approved by the Study Medical Monitor. If a patient is taking doxycycline or TUCA they should discontinue treatment at least 4 days prior to Study Day 1.

Treatment with either Vyndaqel[®] or Diflunisal is not allowed at any time during the treatment period and ideally should not be taken during the post-treatment follow-up period. If Vyndaqel[®] or Diflunisal are taken in the post-treatment period, the Study Medical Monitor should be consulted to determine if an additional mNIS+7 assessment should be collected prior to initiating Vyndaqel[®] or Diflunisal treatment.

Due to known potential adverse effects of nonsteroidal anti-inflammatory drugs (NSAIDs), angiotensin-converting enzyme (ACE) inhibitors, and angiotensin II receptor blockers (ARBs) on renal function, it is recommended that they should be used with caution. Discussion with the Sponsor Medical Monitor prior to initiation of drugs that may affect renal function is recommended.

8.10.2 Concomitant Procedures

A concomitant procedure is any therapeutic intervention (e.g., surgery/biopsy, physical therapy) or diagnostic assessment (e.g., blood gas measurement, bacterial cultures) performed between signing of informed consent and Week 91 visit.

8.11 Treatment Compliance

Compliance with treatment dosing is to be monitored and recorded by Study Center staff.

The Study Center staff is required to document the receipt, dispensing, and return of Study Drug supplies. Patients that are self-administering Study Drug at home must record treatment in a provided dosing diary that will be reviewed by the Study Center staff and Clinical Monitor.

9. SERIOUS AND NON-SERIOUS ADVERSE EVENT REPORTING

9.1 Sponsor Review of Safety Information

Safety information will be collected, reviewed, and evaluated by the Sponsor in accordance with the Safety Management Plan throughout the conduct of the clinical trial.

9.2 Regulatory Requirements

The Sponsor is responsible for regulatory submissions and reporting to the Investigators of serious adverse events (SAEs) including SUSARs per the International Conference on

Harmonization (ICH) guidelines E2A and ICH E6. Country-specific regulatory requirements will be followed in accordance with local country regulations and guidelines.

IRB/IEC will be notified of any SAE according to applicable regulations. The Data and Safety Monitoring Board (DSMB) will be notified of any SAE as specified in the DSMB charter.

The Sponsor will evaluate the available information and decide if there is a reasonable possibility that the Study Drug caused the AE and, therefore, meets the definition of a SUSAR.

Appropriate personnel at the Sponsor will unblind SUSARs for the purpose of regulatory reporting. The Sponsor will submit SUSARs to Regulatory Agencies in blinded or unblinded fashion according to local law. The Sponsor will submit SUSARs to Investigators in a blinded fashion.

For Study Drug “expected” events, refer to the Investigator Brochure.

9.3 Definitions

9.3.1 Adverse Event

An adverse event is any unfavorable and unintended sign (including a clinically-significant abnormal laboratory finding, for example), symptom, or disease temporally associated with the study or use of investigational drug product, whether or not the AE is considered related to the investigational drug product.

9.3.2 Adverse Reaction and Suspected Adverse Reaction

An adverse reaction is any adverse event caused by the Study Drug.

A suspected adverse reaction is any adverse event for which there is a reasonable possibility that the drug caused the adverse event. A suspected adverse reaction implies a lesser degree of certainty about causality than an adverse reaction.

9.3.3 Serious Adverse Event (SAE)

A serious adverse event is any adverse event that in the view of either the Investigator or Sponsor, meets any of the following criteria:

- Results in death
- Is life threatening: that is, poses an immediate risk of death at the time of the event

An AE or suspected adverse reaction is considered “life-threatening” if, in the view of either the Investigator or Sponsor, its occurrence places the patient at immediate risk of death. It does not include an AE or suspected adverse reaction that, had it occurred in a more severe form, might have caused death.

- Requires inpatient hospitalization or prolongation of existing hospitalization

Hospitalization is defined as an admission of greater than 24 hours to a medical facility and does not always qualify as an AE.

- Results in a persistent or significant incapacity or substantial disruption of the ability to conduct normal life functions
- Results in congenital anomaly or birth defect in the offspring of the patient (whether the patient is male or female)
- Important medical events that may not result in death, are not life-threatening, or do not require hospitalization may also be considered serious when, based upon appropriate medical judgment, they may jeopardize the patient and may require medical or surgical intervention to prevent 1 of the outcomes listed in this definition. Examples of such medical events include allergic bronchospasm requiring intensive treatment in an emergency room or at home, blood dyscrasias or convulsions that do not result in inpatient hospitalization, or the development of drug dependency or drug abuse.

9.4 Monitoring and Recording Adverse Events

Any pre-existing conditions or signs and/or symptoms present in a patient prior to the start of the study (i.e., before informed consent) should be recorded as Medical History and not recorded as AEs unless the pre-existing condition worsened. The Investigator should always group signs and symptoms into a single term that constitutes a **single unifying diagnosis** if possible.

9.4.1 Serious Adverse Events

In the interest of patient safety, and in order to fulfill regulatory requirements, all SAEs (regardless of their relationship to Study Drug) should be reported to the Sponsor or designee within 24 hours of the Study Center's first knowledge of the event. The collection of SAEs will begin after the patient signs the informed consent form and stop at the end of the patient's follow-up period which is defined as the Week 91 visit or the EOT efficacy assessment for patients that will enroll into the OLE. When the Investigator is reporting by telephone, it is important to speak to someone in person versus leaving a message. An Initial Serious Adverse Event Form should be completed and a copy should be faxed to the Sponsor or designee.

Detailed information should be actively sought and included on Follow-Up Serious Adverse Event Forms as soon as additional information becomes available. All SAEs will be followed until resolution. SAEs that remain ongoing past the patient's last protocol-specified follow-up visit will be evaluated by the Investigator and Sponsor. If the Investigator and Sponsor agree the patient's condition is unlikely to resolve, the Investigator and Sponsor will determine the follow-up requirement.

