6.1.4 Post-Treatment Period

After completion of the EOT efficacy assessment, patients will enter the 6-month post-treatment evaluation period and will report to the study center and have weekly platelet monitoring for a minimum of 6 weeks after the last dose of Study Drug which may be collected by the clinic, Sponsor's home healthcare service or by a local laboratory as outlined in the schedule of procedures (Appendix A). At Week 71, adverse events should be collected by the site personal through a phone contact with the patient if a clinic visit was not conducted.

Alternatively, after completion of the EOT efficacy assessment, eligible patients may elect to receive ISIS 420915 in an OLE study (ISIS 420915-CS3), pending study approval by the IRB/IEC and the appropriate regulatory authority. In this case, patients will not participate in the post-treatment evaluation period but weekly platelet monitoring should continue between the last dose of Study Drug in CS2 and the first dose of Study Drug in CS3. If this period extends beyond 6 weeks, the frequency will be determined by the Study Medical Monitor.

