8.5.4 Safety Monitoring Rules for Platelet Count Results

Platelets will be monitored weekly throughout the treatment period and for a minimum of 6 weeks after the last dose of Study Drug (this includes early termination patients as well as patients that complete the full 65-week treatment period). For patients participating in the Post-Treatment Evaluation Period, frequency of testing after the Week 71 visit will be determined by the Investigator in consultation with the Study Medical Monitor. For patients participating in the ISIS 420915-CS3 study, weekly monitoring should continue between the last dose of Study Drug in CS2 and first dose of Study Drug in CS3. If this period extends beyond 6 weeks, the frequency of monitoring will be determined by the Study Medical Monitor.

All platelet count results must be promptly reviewed by the Investigator to ensure that the count has not met the stopping rule.

If for any reason there is more than 14 days between platelet values (e.g., lab report of an unreadable sample due to clumping, hemolysis, or quantity not sufficient, or a missed lab assessment), the Investigator will contact the patient to hold dosing until a new platelet value is obtained and reviewed.

If a patient's platelet counts fall below $100,000/\text{mm}^3$, additional lab tests may be requested as determined by the Investigator in consultation with the Study Medical Monitor.

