9.4.2 Non-Serious Adverse Events

The recording of non-serious AEs will begin after the patient signs the informed consent form and will stop at the end of the patient's follow-up period, which is defined as the Week 91 visit, or the EOT efficacy assessment for patient's that will enroll into the OLE. The Investigator will monitor each patient closely and record all observed or volunteered AEs on the Adverse Event Case Report Form.

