 - The baseline laboratory assessment including PD will be defined as the average of all non-missing pre-dose assessments.

- The baseline for all other assessments will be defined as the last non-missing value prior to the first dose of Study Drug.
- For efficacy endpoints except for BMI and mBMI:
 - The efficacy on-treatment period spans the time during which the study treatment is administered until 52 days after the last dose of medication.
 - The efficacy post-treatment period starts on the day after the efficacy on-treatment period and ends on the day of the patients's last contact date within the study.
- For BMI, mBMI and PD endpoints:
 - The on-treatment period spans the time during which the study treatment is administered until 28 days after the last dose of medication.
 - The on-post-treatment period starts on the day after the on-treatment period and ends on the day of the patient's last contact date within the study.
- For safety endpoints except ERG:
 - The safety on-treatment period spans the time during which the study treatment is administered until 7 days after the last dose of medication.
 - The safety post-treatment period starts on the day after the safety treatment period and ends on the day of the patient's last contact date within the study.
 - The safety on-study period spans the time drug is first administered until the day of the patient's last contact date within the study.
- For ERG:
 - The on-treatment period spans the time during which the study treatment is administered until 28 days after the last dose of medication.
 - The post-treatment period starts on the day after the on-treatment period and ends on the day of the patient's last contact date within the study.
- The PK and Immunogenicity (IM) on-study period spans the time drug is administered until the day of the patient's last contact date within the study.
- Note: Assessments for mNIS+7, NSC, ERG, and ophthalmology done early in the treatment period that are used for baseline cannot also be used as an on-treatment assessment.
- Body mass index (BMI) will be computed using the formula:

$$\text{BMI} = (\text{weight in kilograms}) / [\text{height in cm} / 100]^2$$
- Modified BMI (mBMI) will be computed from BMI and serum albumin levels by:

$$\text{mBMI} = \text{BMI} * \text{serum albumin (g/L)}.$$

- Duration of study drug exposure will be derived as the difference between the date of the last dose of study drug and the date of the first dose plus one.

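### For OLE-bound patients, CS2 adverse event collection stops at the EOT assessment, while CS2 platelet monitoring continues to the first CS3 dose

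*Protocol*

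**What the plan says.** Two sets of provisions apply to a patient who completes treatment and goes on to the OLE (ISIS 420915-CS3).

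**Event collection.** Protocol 9.4.1 collects SAEs from consent to the end of follow-up, "which is defined as the Week 91 visit or the EOT efficacy assessment for patients that will enroll into the OLE". Section 9.4.2 sets the same end for non-serious events: Week 91, "or the EOT efficacy assessment for patient's that will enroll into the OLE".

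**Platelet surveillance.** Section 6.1.4 takes the OLE patient out of post-treatment follow-up but adds that "weekly platelet monitoring should continue between the last dose of Study Drug in CS2 and the first dose of Study Drug in CS3". Section 8.5.4 and Appendix A footnote 10 repeat this requirement. No maximum is set; 8.5.4 provides that "If this period extends beyond 6 weeks, the frequency of monitoring will be determined by the Study Medical Monitor".

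The Week 71 adverse event phone contact in 6.1.4 belongs to the post-treatment period, so it does not reach these patients. No section extends AE or SAE collection to the first CS3 dose.

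**Analysis.** SAP 3.2.1.1 states: "The safety on-treatment period spans the time during which the study treatment is administered until 7 days after the last dose of medication". SAP 3.2.1.4 and 3.9 also plan an on-study table of all treatment-emergent events, including those starting more than 7 days after the last dose. SAP 3.9.2 plans risk differences with confidence intervals for AEs of special interest and other AEs of interest, which include thrombocytopenia and haemorrhages.

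**The concern.** Amendment 9 brought in weekly platelet counts after severe thrombocytopenia in this study, including one fatal intracranial bleed. By carrying those counts into the interval between CS2 and CS3, the protocol treats the patients there as still at risk. Over the same interval it withdraws the general duty to record adverse events and to report serious ones within 24 hours.

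A platelet count does not stand in for that duty. Section 8.6.3 itself interprets a count below 75,000/mm³ according to whether bleeding is present, and bleeding is the information no longer collected. The SAP's abnormal platelet tables run to the patient's last contact in the study. A low count could therefore appear in CS2 without the clinical event that went with it. The documents do not say whether counts taken in the interval belong to CS2 or to CS3.

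**Working it through.** There is no power or alpha figure to reproduce; the check is day arithmetic on the schedule.

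**Inputs**
- Appendix A: last scheduled dose Day 449 (Week 65), EOT Day 456 (Week 66), Week 71 Day 491, Week 91 Day 631.
- Protocol 6.1.3: two EOT assessments on separate days, the first more than about 24 hours after the last dose, both within 14 days of it.
- Protocol 8.5.4: platelets for at least 6 weeks after the last dose.
- SAP 3.2.1.1: on-treatment safety window closes 7 days after the last dose.

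**Calendar check.** Day = (week − 1) × 7 + 1 gives Week 66 = 456, Week 71 = 491 and Week 91 = 631, as printed. The 6-week platelet minimum ends on 449 + 42 = Day 491, which is the Week 71 visit. The schedule is internally consistent.

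**AE follow-up after the last dose**
- OLE-bound, nominal: 456 − 449 = 7 days.
- OLE-bound, earliest: the second assessment can finish at about Day 451, so 451 − 449 = about 2 days.
- OLE-bound, latest: 14 days (Day 463).
- Not entering the OLE: 631 − 449 = 182 days.

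**Interval without CS2 AE collection.** The CS3 start day is not given. Assuming it falls 6 weeks after the last dose (Day 491):
- nominal EOT: 491 − 456 = 35 days;
- EOT finished at the 14-day limit: 491 − 463 = 28 days;
- EOT finished early: 491 − 451 = about 40 days.

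An immediate CS3 start brings the interval close to zero; a start after 6 weeks lengthens it. Within the 6-week case, five weekly platelet checks (Weeks 67 to 71) follow the nominal EOT with no AE collection beside them.

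**SAP on-treatment window.** It closes on 449 + 7 = Day 456, the nominal EOT day. A nominal or later EOT loses nothing. An EOT finished at about Day 451 loses 456 − 451 = about 5 days.

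**Duties that survive the cut-off**
- 8.6.3: 24-hour notice to the Study Medical Monitor of a local platelet count below 50,000/mm³.
- 9.4.1: follow-up of SAEs already reported.
- 6.2.5: supplemental CRF pages for listed events, including death and cerebrovascular events, with no OLE cut-off stated.
- 8.5.4 and 9.5.1: investigator review of platelet results and monitoring of clinically significant laboratory abnormalities.

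None of these is a general requirement to collect a new bleed or hospital admission, or to report it as an SAE within 24 hours.

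**The case against.** The strongest objection is that CS3 may collect events from its own consent, which could shrink or close the interval. That stands as a limit. A reader might infer that serious events here go unreported to the sponsor and the DSMB, and the documents do not support this. They show only that CS2 stops collecting; the CS3 protocol is not available.

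The surviving duties listed above are also real, so it would be too strong to say that a site has no CS2 obligation at all. They are narrower than SAE reporting.

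Because the cut-off turns on intention to enroll, a reader might infer that collection is closed for good for a patient who then changes their mind. The synopsis and 6.1.4 largely answer this: post-treatment follow-up is the default and the OLE is the alternative, so someone who does not enroll belongs to the Week 91 group. The wording needs clarifying, no more.

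Three further inferences go beyond the documents:
- That the interval covers most of the drug's washout. The half-lives in 2.3.3 are nonclinical, and no interval length is given.
- That most completers are affected. OLE uptake is not stated.
- That the cut-off is what makes off-drug safety data selective. Any optional extension that re-doses patients does this, and moving the cut-off would not remove it.

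Finally, platelets may be drawn by home healthcare or a local laboratory, so an AE question is not automatically available at each draw. That is a fair point about cost, and the fix allows for it.

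**Conclusion.** The concern holds in a limited form. Sections 9.4.1 and 9.4.2 do not fit with 6.1.4, 8.5.4 and footnote 10: for OLE-bound patients, CS2 requires platelet surveillance over an interval in which it no longer collects new adverse events. This is an explicit cut-off, not an omitted detail, and it should be changed.

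Its size depends on when CS3 starts: near zero for an immediate start, 28 to about 40 days (nominally 35) for an assumed start at 6 weeks, and longer after that. The effect on the SAP's on-treatment AE tables is small, 0 to about 5 days per patient. The on-study table and the thrombocytopenia and haemorrhage summaries are more exposed. The conclusion covers events that begin after EOT and their capture in CS2 only.

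**What to change.** In 9.4.1 and 9.4.2, end AE and SAE collection for OLE patients at the first dose of Study Drug in CS3, or at Week 91 if no CS3 dose is given. Tying the end to a dose rather than to a plan to enroll also settles the case of the patient who does not go on. Reconcile the wording with 6.1.4, 8.5.4 and Appendix A footnote 10, and state which study's database holds events in the interval.

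Events can be asked about at contacts that already take place. Where platelets are drawn by home healthcare or a local laboratory, a site phone call would serve, as 6.1.4 already provides at Week 71.

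The cost is amendment wording, a few phone contacts per patient, and a rule to prevent the same event being entered in both CS2 and CS3. No new visits or tests are needed, and no treatment or monitoring rule changes.

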9.4.2 Non-Serious Adverse Events

The recording of non-serious AEs will begin after the patient signs the informed consent form and will stop at the end of the patient's follow-up period, which is defined as the Week 91 visit, or the EOT efficacy assessment for patient's that will enroll into the OLE. The Investigator will monitor each patient closely and record all observed or volunteered AEs on the Adverse Event Case Report Form.

9.4.3 Evaluation of Adverse Events (Serious and Non-Serious)

The Investigator's opinion of the following should be documented on the Adverse Event Case Report Form:

9.4.3.1 Relationship to the Study Drug

The event's relationship to the Study Drug is characterized by 1 of the following:

- **Related:** There is clear evidence that the event is related to the use of Study Drug e.g., confirmation by positive re-challenge test
- **Possible:** The event cannot be explained by the patient's medical condition, concomitant therapy, or other causes, and there is a plausible temporal relationship between the event and Study Drug administration
- **Unlikely/Remote:** An event for which an alternative explanation is more likely (e.g., concomitant medications or ongoing medical conditions) or the temporal relationship to Study Drug administration and/or exposure suggests that a causal relationship is unlikely (For reporting purposes, Unlikely/Remote will be grouped together with Not Related)
- **Not Related:** The event can be readily explained by the patient's underlying medical condition, concomitant therapy, or other causes, and therefore, the Investigator believes no relationship exists between the event and Study Drug

9.4.3.2 Severity

The event's severity is characterized by 1 of the following:

- **Mild:** The event is easily tolerated by the patient and does not affect the patient's usual daily activities
- **Moderate:** The event causes the patient more discomfort and interrupts the patient's usual daily activities
- **Severe:** The event is incapacitating and causes considerable interference with the patient's usual daily activities

If the event is an SAE, then all applicable seriousness criteria must be indicated (criteria listed in Section 9.3.3).

